3.4 Enrollment on Study at Collaborating Sites

Collaborating Site research participants should be registered at St. Jude within 24 hours of enrollment at the site. The completed Eligibility Checklist and entire signed Informed Consent should be faxed to [REDACTED]. Please call [REDACTED] if confirmation of the enrollment information is needed. The Protocol Eligibility Coordinator will then register the research participant in the Patient Protocol Manager (PPM) system.

4.0 TREATMENT PLAN

4.1 Overview

Patients must have fully recovered from the acute effects of all prior therapy before starting selinexor. In addition, at least 14 days must have elapsed since the completion of myelosuppressive therapy or gemtuzumab ozogamicin and the first dose of selinexor. At least 24 hours must have elapsed since the completion of low-dose or non-myelosuppressive therapy, such as hydroxyurea, vincristine, steroids, or low-dose cytarabine (up to 100 mg/m²/day), and the first dose of selinexor. For patients who have received prior HSCT, there can be no evidence of GVHD and greater than 60 days must have elapsed since the HSCT.

This study will include two phases. The dose-escalation phase will characterize the dose-limiting toxicities (DLTs) and determine the maximum tolerated dose (MTD) and recommended phase 2 dose (RP2D) of selinexor when given in combination with fludarabine and cytarabine. The RP2D will be chosen based on the MTD and totality of the data (clinical, PK, and PD data from this and other trials). The phase II cohort will further assess the safety and will explore the efficacy of this combination.

Selinexor will be given orally on days 1, 3, 8, 10, 22 and 24 of each cycle.

Fludarabine (30 mg/m²/dose IV over 30 minutes daily) and **cytarabine** (2 gram/m²/dose IV over 4 hours daily) will be given on days 16 (\pm 2 days) through 20 (\pm 2 days). Chemotherapy may be delayed if clinically indicated.

For patients who achieve CR or CRi with negative MRD or with MRD that has decreased at Day 15, the treating physician may continue single agent selinexor without fludarabine and cytarabine. In this case, selinexor should be given on days 1, 3, 8, 10, 15, 17, 22 and 24.

Patients who achieve CR or CRi status (as defined in Section 8.1) at day 15 (regardless of MRD status) may proceed directly to HSCT at the discretion of the treating physician.

Fludarabine and cytarabine may be given before Day 16 if the treating physician, after consulting with the principal investigator (PI), believes it is in the patient's best interest based on disease progression. In general, the fludarabine/cytarabine combination should begin prior to day 16 if the leukocyte count is greater than 50,000/ μ l and increases by >50%. For example, if the leukocyte count is 30,000/ μ l and increases to 46,000/ μ l, fludarabine and cytarabine will start on day 16 as planned. However, if the leukocyte count is 60,000/ μ l and increases to 91,000/ μ l, fludarabine and cytarabine may be started early.

Note that these are guidelines that should be used in the context of each patient's clinical condition.

If fludarabine and cytarabine are given prior to Day 16, the administration of selinexor should be held at start of fludarabine and cytarabine administration and resumed 3 days after completion of fludarabine and cytarabine to complete total of three weeks of selinexor during course one.

Diagnostic lumbar puncture and **intrathecal (IT) chemotherapy** should be given prior to cycle 1, but may be delayed if clinically indicated. IT cytarabine, IT methotrexate, and IT methotrexate/ hydrocortisone/cytarabine (MHA) are all acceptable. Note that the first dose of IT chemotherapy may be given prior to or after enrollment on SELHEM.

Patients without evidence of central nervous system (CNS) leukemia will receive no further IT therapy during cycle 1. Patients with CNS disease (defined as the presence of any blasts in the CSF) will receive weekly ITMHA until the cerebrospinal fluid becomes free of leukemia.

For patients who require IT therapy on day 15, administration of IT therapy should be separated from administration of IV fludarabine and cytarabine by at least one day.

4.2 Intrathecal Chemotherapy

Patient Age	Methotrexate	Hydrocortisone	Cytarabine	Volume
< 1 year	6 mg	12 mg	18 mg	6 ml
1-2 years	8 mg	16 mg	24 mg	8 ml
2-3 years	10 mg	20 mg	30 mg	10 ml
> 3 years	12 mg	24 mg	36 mg	12 ml

Leucovorin rescue (5 mg/m²/dose, max 5 mg) PO will be given at 24 and 30 hours after each triple intrathecal treatment. Follow plasma methotrexate levels (starting 24 hours after intrathecal therapy and until level becomes undetectable) in patients with renal dysfunction or extra fluid in third space, and rescue with leucovorin as clinically indicated.

4.3 Dose-Escalation Cohort (*completed*)

As described above, the starting dose of selinexor will be 30 mg/m²/dose, which is well below the current adult Phase I dose (trial KCP-330-001) of 70 mg/m² which has cleared DLT and below the adult Phase II dose of 55 mg/m² (trial KCP-330-008).

Selinexor, initially at 30 mg/m²/dose, will be given twice weekly (on days 1 and 3) and escalated or de-escalated based on tolerability (Dose level -1, 1, 2, and 4 are shown in Table 3 below). The rolling-6 design will be used for the conduct of this study.

A full safety evaluation will be conducted when participants have completed 28 days of therapy. Only cycle 1 of therapy will be used to evaluate the DLT.

Two to 6 participants can be concurrently enrolled onto a dose level, dependent on:

- 1) the number of participants enrolled at the current dose level, and
- 2) the number of participants who have experienced DLT at the current dose level, and
- 3) the number of participants entered but with tolerability data pending at the current dose level.

Accrual is suspended when a cohort of 6 has enrolled or when the study endpoints have been met.

The decision as to which dose level to enroll a participant is based on the number of participants currently enrolled and evaluable, the number of participants experiencing DLT, and the number of participants still at risk of developing a DLT at the time of new participant entry. For example, when 3 participants are enrolled onto a dose level, if toxicity data is available for all 3 participants and no DLTs are observed when the 4th participants enter, the dose is escalated and the 4th participants is enrolled to the next higher dose level; if toxicity data is not yet available for 1 or more of the three participants and no DLT has been observed, or if 1 DLT has been observed, the new participant is entered at the same dose level; if 2 or more DLTs have been observed from the 3 participants, the dose level is de-escalated. This process is repeated for the 5th and 6th participants.

Table 3. Dose-escalation plan

Dose level	Selinexor (mg/m ² /dose on days 1, 3, 8, 10, 22 and 24)	Fludarabine (mg/m ² /dose on days 16-20)	Cytarabine (g/m ² /dose on days 16-20)
-1	20	30	2
1	30	30	2
2	40	30	2
3	55	30	2
4	70	30	2

4.4 Phase II Cohort

The Phase II portion of the study will enroll patients at a **selinexor dose of 40 mg/m²/dose** on the same administration schedule as the dose escalation cohort.

Evaluation of response to single agent selinexor: unless there is evidence of progressive disease by examination of the blood, participants should undergo bone marrow evaluation on day 15 (\pm 2 days). This evaluation must be performed prior to administration of fludarabine and cytarabine.

Evaluation of response to Cycle 1: participants should undergo response evaluation between days 42 and 56 of Cycle 1 (with the exception of any patient who obtains complete response at Day15 and elects to continue single agent selinexor and forego fludarabine and cytarabine therapy). Patients may be evaluated earlier if there is evidence of hematopoietic recovery or at discretion of treating physician. In cases with hypocellular marrows (<10% cellularity), repeat bone marrow examinations should be considered when there is evidence of hematopoietic recovery.

Table 4. Treatment administration

Drug	Dose	Route	Schedule
Selinexor	40 mg/m ²	PO	Days 1, 3, 8, 10, 22 and 24
Fludarabine	30 mg/m ² /dose	IV over 30 minutes	Days 16-20 ^a
Cytarabine	2 gram/m ² /dose	IV over 4 hours ^b	Days 16-20 ^a

^a *May be given earlier or later, as clinically indicated*

^b *Cytarabine should start at least 3.5 hours after completion of fludarabine*

Selinexor should be administered with food or within 30 minutes after a meal. The dose will be determined according to Appendix I and rounded to the nearest 10 mg.

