Appendix I: Selinexor Dose Rounding Chart

Appendix II: Performance Status Criteria

Appendix III: Tests Performed for Routine Care and for Research

Appendix IV: Selinexor Dose Modification Guidelines for AEs Associated with Selinexor

Appendix V: Specimen Submission Guidelines

1.0 OBJECTIVES

1.1 Primary Objective

- 1.1.1 To determine a tolerable combination of selinexor, fludarabine, and cytarabine in pediatric patients with relapsed or refractory hematologic malignancies including acute myeloid leukemia (AML), acute lymphoblastic leukemia (ALL), mixed phenotype acute leukemia (MPAL) and myelodysplastic syndrome (MDS) in the phase I portion of the study.
- 1.1.2 To estimate the overall response rate, as defined by complete response or complete response with incomplete count recovery, of selinexor in combination with fludarabine and cytarabine for patients with relapsed or refractory AML in the phase II portion of the study.

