4.7.1 Cycle 2 combination therapy

Participants may begin Cycle 2 combination therapy when the absolute neutrophil count (ANC) is $\geq 300/\mu\text{l}$ and rising and the platelet count $\geq 30,000/\mu\text{l}$ and rising.

- Selinexor (40 mg/m²/dose) will be given orally on days 1, 3, 8, 10, 22 and 24 at the same dose that was given in Cycle 1.
- Fludarabine (30 mg/m²/dose IV over 30 minutes daily) on days 15-19
- Cytarabine (2 gram/m²/dose IV over 4 hours daily) will be given on days 15-19

Combination therapy will be limited to a maximum of 2 cycles.

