5.0 DRUG INFORMATION

5.1 SELINEXOR (KPT-330)

Description: Selinexor is a selective inhibitor of nuclear export (SINE). Selinexor specifically blocks XPO1-mediated nuclear export by forming a slowly reversible covalent bond with the nuclear export protein XPO1.

Selinexor is manufactured by KABS Laboratories (Montreal, ON) for Karyopharm, Therapeutics (Newton, MA) using methods in accordance with Food and Drug Administration (FDA) guidelines for the manufacture and testing of antineoplastic agents for human use. Selinexor is an investigational agent supplied to investigators by Karyopharm Therapeutics.

Selinexor will be supplied as clear-coated tablets for oral use in two (2) dose strengths: 10 and 25 mg of active ingredient per tablet. Bulk bottles of 50 tablets per bottle will be supplied for each of the two strengths. Tablets of selinexor should not be crushed because of increased risk of dermatologic toxicity if powder comes in contact with skin. Selinexor will be available in 20 mg strength tablets, provided in blister packs, as an additional option for patients in the future.

Storage and stability: Tablets of selinexor drug product will be stored at ambient temperature in white HDPE bottles, in a locked and secured area with restricted access. Selinexor tablets can be stored long term between 5 and 30 °C, but should not be stored frozen or at freezer temperatures. Room temperature storage is recommended.

Stability of tablets: Selinexor tablets are currently in on-going stability studies. The current expiry is 30 months for the 10 mg and 25 mg bottled samples and 21 months for the blister-packed 20 mg tablets, and will be extended when further stability data becomes available.

Handling: Qualified personnel, familiar with procedures that minimize undue exposure to themselves and the environment, should undertake the preparation, handling, and safe disposal of the chemotherapeutic agent in a self-contained and protective environment.

Supplier: Selinexor is an investigational agent and will be supplied free-of-charge from Karyopharm Therapeutics, Inc.

Administration: Selinexor tablets for oral administration should be taken within 30-minutes of food consumption.

Each dose will consist of selinexor for oral administration based on mg/m² basis, and should be based on the patient's actual body surface area (BSA) calculated at baseline (Cycle 1) and at the start of each subsequent cycle. See Appendix I for Dosing Guidelines

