APPENDIX I: SELINEXOR Dosing Guidelines

Phase II Cohort: Dose Level 2 (40 mg/m²)

BSA range	Total mg dose
0.45 – 0.55	20
0.56 – 0.68	25
0.69 – 0.81	30
0.82 – 0.93	35
0.94 – 1.06	40
1.07 – 1.18	45
1.19 – 1.31	50
1.32 – 1.43	55
1.44 – 1.56	60
1.57 – 1.68	65
1.69 – 1.81	70
1.82 – 1.93	75
1.94 – 2.06	80
2.07 – 2.18	85
2.19 – 2.31	90
2.32 – 2.43	95
2.44 and greater	100

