Grade 1	5-HT ₃ antagonists, D ₂ antagonists, olanzapine 1.25 to 5mg daily, corticosteroids (e.g., dexamethasone 5-10 mg/m ² /day with each dose of selinexor ± the day after dosing), NK ₁ antagonists, or dronabinol (Marinol) or combinations can prevent nausea in the majority of patients.
Grade 2	Implement one or more combinations of anti-nausea medications. If nausea does not resolve to Grade ≤ 1, reduce dose of selinexor by one dose level (Table A2.1).
Grade 3	Implement one or more combinations of anti-nausea medications and interrupt dosing of selinexor. selinexor may be restarted with one dose level reduction (Table A2.1) when nausea is Grade ≤ 2 and adequate caloric and fluid intake have been achieved.

Hyponatremia (common)	
Grade 1 (Lower Limit of Normal to 130 nM)	Be certain sodium level is corrected for hyperglycemia (serum glucose >150mmol/L). Rule out other causes of low sodium (e.g., cardiac, hepatic, adrenal, renal and thyroid diseases, SIADH), Fanconi Syndrome, hyperglycemia, diuretic use). Maintain selinexor dose level, assure adequate fluid, electrolyte and caloric intake, adjust other medications, consider salt supplementation one – two times per day.
Hyponatremia 126-129nM without Symptoms (Grade 3)	Be certain sodium level is corrected for hyperglycemia. Rule out other causes of low sodium (e.g., cardiac, hepatic, adrenal, renal and thyroid diseases, SIADH), Fanconi Syndrome, hyperglycemia, diuretic use). Hold selinexor until Grade ≤ 1 (≥ 130 nM) and initiate aggressive salt supplementation two-three times per day.
Grade 3 (120-125 nM) or any Grade 3 with Symptoms	Be certain sodium level is corrected for hyperglycemia. Rule out other causes of low sodium (e.g., cardiac, hepatic, adrenal, renal and thyroid diseases, SIADH), Fanconi Syndrome, hyperglycemia, diuretic use). Hold selinexor until resolved to Grade ≤ 1 (≥ 130 nM) then reduce selinexor dose by 1 level. Initiate aggressive salt supplementation two-three times per day. If serum sodium stabilizes for at least 4 weeks, then original dose of selinexor may be resumed.
Diarrhea (common)	
Grade 1 (despite maximal anti-diarrheal medication)	At the first sign of abdominal cramping, loose stools, or onset of diarrhea, it is recommended that the patient be treated according to institutional standard of care, e.g., loperamide (Immodium®). Maintain dose level of selinexor.

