Grade 2 (despite maximal anti-diarrheal medication)	Reduce to selinexor to one weekly until resolved to \leq Grade 1, then re-start twice weekly at the current dose level. If diarrhea returns as \geq Grade 2, then reduce selinexor dose by one dose level and dose once weekly until resolved to \leq Grade 1, then re-start twice weekly at reduced dose level
Grade 3/4 (despite maximal anti-diarrheal medication)	Delay selinexor until resolved to \leq Grade 2, then follow guidelines above.
Thrombocytopenia	
Grade 3 Thrombocytopenia Without bleeding	Implement platelet growth factors or transfusions. Begin (or maintain) once weekly dosing at the same dose level until resolved to Grade ≤ 2 .
Grade 4 Thrombocytopenia Without bleeding	Implement platelet growth factors or transfusions. Hold dosing until Grade ≤ 3 and follow above guidelines if Grade 3.
\geq Grade 3 Thrombocytopenia associated with petechiae or purpura	Implement platelet growth factors and/or transfusions. Hold selinexor for 5 days after last bleeding. Restart dosing one dose level below.
Neutropenia	
Grade 3 neutropenia without fever	Implement growth factors.
Grade 4 neutropenia without fever	Implement growth factors. If appropriate, initiate prophylactic anti- microbial agents.
Grade ≥ 3 febrile neutropenia	Implement growth factors. Initiate appropriate broad spectrum anti- microbial agents. Hold selinexor until fever resolves and patient is clinically stable. Restart dosing one dose level below.

Other selinexor-related adverse events	
Grade 1 or 2	Maintain dose level and initiate standard supportive care.
Grade 3	Delay dose until resolved to \leq Grade 1, then reduce by 1 dose level (Table A2.1).
Grade 4	Discontinue selinexor and rule out other causes. If other causes of Grade 4 adverse event are uncovered, selinexor may be re-initiated at 1 dose level reduction (Table A2.1).

All dose modifications should be based on the worst preceding toxicity. Isolated values of \geq Grade 3 alkaline phosphatase values will NOT require dose interruption. Determination of liver vs. bone etiology should be made, and evaluation of gamma-glutamyl transferase (GGT), 5'-nucleotidase (5'NT), or other liver enzymes should be performed. Patients are allowed dose reductions to a minimum dose of 15 mg/m² as described in Table A2.1. a. Common Terminology Criteria for Adverse Events (CTCAE Version 4.03) otherwise specified values.
	

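### Section 4.4 says to round Phase II selinexor to 10 mg, but the Appendix I chart it cites moves in 5 mg steps; the Cycle 2 dose is also unclear for patients reduced in Cycle 1

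*Combined protocol and SAP*

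**What the plan says.** **Starting dose.** Section 4.4 fixes Phase II selinexor at 40 mg/m² and adds: "The dose will be determined according to Appendix I and rounded to the nearest 10 mg". The chart in Appendix I is headed "Phase II Cohort: Dose Level 2 (40 mg/m²") and has 17 rows, from 20 mg at BSA 0.45–0.55 m² to 100 mg at 2.44 m² and above, in 5 mg steps. The list of appendices names it "Appendix I: Selinexor Dose Rounding Chart". Section 5.1 bases each dose on actual BSA, recalculated every cycle, and refers to Appendix I without any 10 mg rule.

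**Tablets.** Section 5.1 supplies "two (2) dose strengths: 10 and 25 mg of active ingredient per tablet", with a 20 mg strength as a further option. It adds: "Tablets of selinexor should not be crushed because of increased risk of dermatologic toxicity".

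**Cycle 2.** Section 4.7.1 puts 40 mg/m² in brackets and then, in the same sentence, says selinexor is given "at the same dose that was given in Cycle 1".

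**Reductions.** Appendix IV orders reductions by one level and ends: "Patients are allowed dose reductions to a minimum dose of 15 mg/m² as described in Table A2.1". Table A2.1 is cited ten times but is not in the supplied text. Table 3 (section 4.3) prints level 2 as 40, level 1 as 30 and level -1 as 20 mg/m². Appendix IV provides for return to the starting dose only in the row for sodium of 120–125 or symptomatic Grade 3 hyponatremia: "If serum sodium stabilizes for at least 4 weeks, then original dose of selinexor may be resumed".

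**The concern.** A pharmacist applying section 4.4 literally has two answers whenever the chart total ends in 5, because such a total is an exact tie under a 10 mg rule and the text does not say which way to go. Section 12.3 counts on four additional participating sites, so practice could differ between them.

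Below 40 mg/m² there is no chart, and the only rounding rule in print is the 10 mg one. At small totals a 10 mg grid is coarse: a child ordered down a level for toxicity could be given the same tablets as before.

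In Cycle 2, a patient whose dose was lowered during Cycle 1 could be put back to 40 mg/m² by one half of the sentence in 4.7.1 and kept lower by the other half.

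**Working it through.** **1. Reproduce the chart.** Inputs: 40 mg/m² (section 4.4) and the Appendix I bands. On a 0.01 m² grid from 0.45 to 2.43 there are 199 values. Rounding 40 × BSA to the nearest 5 mg returns the chart total at every value except 0.56 (40 × 0.56 = 22.4, which rounds to 20; the chart gives 25). The chart is therefore in effect a 5 mg rounding chart.

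**2. Apply the 10 mg rule to the starting dose.** All disagreements fall in the bands whose total ends in 5. The 25 mg band (0.56–0.68) has 13 grid values, and the seven bands for 35, 45, 55, 65, 75, 85 and 95 mg have 12 each:

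13 + 7 × 12 = 97, and 97/199 = 49%.

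The gap is always 5 mg. At BSA 0.60, 40 × 0.60 = 24 rounds to 20; at 0.65, 40 × 0.65 = 26 rounds to 30; the chart gives 25 for both. In relative terms it is 5/25 = 20%, 5/35 = 14%, falling to 5/95 = 5%. No tie occurs on this grid, so the count does not depend on a tie rule.

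**3. Carry the 10 mg rule to reduced levels.** This step needs two assumptions: that the section 4.4 rule extends below 40 mg/m², and that the ladder is 40, 30, 20, 15 mg/m² (Table 3 plus the Appendix IV floor). Halves are rounded up; rounding them down moves some interval edges by 0.01.

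| Step (mg/m²) | Rounding used | BSA (m²) where the total is unchanged | Grid values |
|---|---|---|---|
| 40 to 30 | Appendix I at 40, 10 mg at 30 | 0.50–0.55 | 6 |
| 40 to 30 | 10 mg at both | 0.50–0.62, 0.84–0.87 | 17 |
| 30 to 20 | 10 mg at both | 0.45–0.49, 0.75–0.83 | 14 |
| 20 to 15 | 10 mg at both | 0.45–0.74, 1.00–1.24, 1.67–1.74 | 63 |

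Examples: at BSA 0.52 the chart gives 20 mg, and 30 × 0.52 = 15.6 rounds to 20. At BSA 1.10, 20 × 1.10 = 22 and 15 × 1.10 = 16.5 both round to 20.

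**4. Check what tablets allow.** Whole 10, 20 and 25 mg tablets make every multiple of 5 from 10 mg upwards except 15 (5 mg is also impossible). Every Appendix I total can therefore be dispensed. Using 5 mg rounding at the reduced levels would not be enough. It changes the total at 40 to 30 and at 30 to 20 for every BSA checked, but 20 to 15 stays unchanged at 0.50–0.62 and 0.84–0.87. It also calls for 15 mg, which cannot be made, for example at 30 mg/m² with BSA 0.45–0.58.

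**5. Cycle 2.** Without a Cycle 1 reduction, both halves of 4.7.1 say 40 mg/m². On the assumed ladder, reading the bracket literally raises the dose by 40/30 − 1 = 33% after one reduction and by 40/20 − 1 = 100% after two.

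**The case against.** The strongest reply is that a sensible reader already knows what to do. Section 4.4 says the dose comes from Appendix I, section 5.1 sends the reader there with no 10 mg rule, and the appendix is listed as a rounding chart. On that reading no starting dose is wrong. This stands as the likely intent, but section 4.4 still tells sites to do both things.

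A reader might infer four stronger claims, which the documents do not support.

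- *About half of patients are misdosed.* The 49% is a share of BSA grid points. No BSA distribution is given, and the differing dose arises only if the chart is overridden.
- *There are no reduction steps.* Table 3 prints 40, 30 and 20, Appendix I labels 40 mg/m² as level 2, and Appendix IV prints the 15 mg/m² floor. Table A2.1 is an unresolved citation in extracted text, not a proven omission.
- *Reductions commonly do nothing.* The intervals rest on the two assumptions in step 3. With the chart at 40, the first reduction fails only at BSA 0.50–0.55, where the tablet-swallowing criterion (3.1.7) probably leaves few patients. The wide intervals belong mainly to a third reduction. Section 2.2 calls 55 mg/m² well tolerated, and no dose reductions are reported.
- *Every patient has two Cycle 2 doses.* Only a patient reduced in Cycle 1 does. Even then, the closing clause of 4.7.1 and the single re-escalation provision in Appendix IV favour carrying the lower dose forward.

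The need for some reductions is still foreseeable. Section 2.1 reports phase I sodium nadirs down to 123 meq/L, inside the Appendix IV band (120–125) that calls for a one-level reduction, although the dose level of that patient is not given and all cases were easily corrected.

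**Conclusion.** The rounding instruction in section 4.4 is wrong as written, because it contradicts the chart it invokes. The size is 5 mg at 97 of 199 grid values, at most 20%, and nil if Appendix I governs.

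The unchanged-reduction problem is conditional on the assumed ladder and on extending the 10 mg rule below 40 mg/m². At the first step, with the chart kept at 40 mg/m², it is confined to BSA 0.50–0.55 m².

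The Cycle 2 ambiguity is real but limited to patients reduced during Cycle 1. These are matters of dosing clarity and safety; they do not enter the Simon stage sizes, cut-offs or error rates.

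**What to change.** 1. **Section 4.4:** delete the clause on rounding to 10 mg, so that Appendix I alone sets the Phase II dose.
2. **Section 4.7.1:** replace the bracketed 40 mg/m² with the last tolerated Cycle 1 dose level, unless Appendix IV permits re-escalation.
3. **Table A2.1:** the sponsor should confirm its steps and make sure the table is included or correctly cited.
4. **Appendix I:** add BSA-to-mg bands for each confirmed reduced level, using only totals that whole tablets can make (no 5 or 15 mg). Once item 1 is done, no rounding rule remains below 40 mg/m² without these bands.

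Items 1 and 2 are text edits with no added patients, procedures or statistical change. Item 4 needs a dosing decision at small BSAs where no suitable lower total exists. At BSA 0.50, for example, the next total below 20 mg is 10 mg, a 50% cut where the assumed ladder orders 25% (40 to 30). Whether to accept that, set a minimum BSA, or hold or stop selinexor is for the sponsor to decide.
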